## 4.3 Study Endpoints

### 4.3.1 Primary Endpoint

Anti-viral effect as measured by the time needed for the viral load to drop below the plaque assay quantification limit (time-to-BQL) in nasal mid-turbinate swab specimens.

### 4.3.2 Secondary Endpoints

- Safety assessment (assessed by physical examination, AEs, laboratory assessments and vital signs) of different doses of ALX-0171
- Change from baseline in Global Severity Score
- Time to clinical response: defined as the time between first administration of study drug and achieving adequate oxygen saturation and oral feeding
- PK properties of ALX-0171
- Viral load profile over time in nasal swab specimens (RT-qPCR and plaque assay)
- Evaluation of serum anti-drug antibodies (ADA)

### 4.3.3 Other Endpoints

- Evolution over time in clinical symptoms (SpO2, feeding, respiratory rate, wheezing, cough, respiratory muscle retractions, and general appearance)
- Evolution over time in RDAI, RACS
- Length of hospital stay defined as time between admission and discharge
- Length of hospital stay for RSV defined as time between admission and discharge excluding prolongation due to SAE other than RSV worsening
- Time between first study drug administration and discharge
- Duration of severe disease, defined as time from admission to hospital to time of clinical response
- Duration of supplemental oxygen therapy
- Duration of feeding support
- Initiation of invasive and non-invasive ventilation and duration of respiratory support
- Transfer to ICU and duration of ICU stay
- Parent(s)/Caregiver(s) assessment of the clinical condition of the subject
- Evolution of serum biomarker over time

## 5 GENERAL ASPECTS FOR STATISTICAL ANALYSIS

### 5.1 Analysis populations

The following populations will be considered for analysis:

#### 5.1.1 All Screened Population

The All Screened population consists of all subjects that were screened during the trial (i.e, subjects with an informed consent form (ICF) (RSV test informed consent and/or study informed consent) signed by parent(s)/legal guardian(s) or legally acceptable representative(s).

#### 5.1.2 Intent-to-treat (ITT) Population

The ITT population consists of all randomized subjects.

### 5.1.3 Modified Intent-to-treat (mITT) Population

The mITT population consists of all randomized subjects who received at least 1 administration of study drug. When using this population, the subjects will be classified as randomized (i.e., using the treatment to which the subject was randomized). This will be the primary study population for the analysis of baseline characteristics, efficacy and pharmacodynamic data.

### 5.1.4 RSV Infected population

The RSV Infected population consists of all randomized subjects with RSV infection, as confirmed by RT-qPCR (hVIVO quantitative PCR assay) on Day 1 (pre- or post-dose), who received at least 1 administration of study drug. Subjects will be classified as randomized when using this population. Dedicated outputs on the RSV infected population will only be created if this population differs from the mITT population.

### 5.1.5 Safety Population

The safety population consists of all subjects who received at least 1 administration of study drug. When using this population, the subjects will be classified as treated (i.e., using the treatment that the subject actually received, see section 5.2). This will be the primary population for the analysis of prior/concomitant medication, exposure, safety and immunogenicity data

### 5.1.6 Per Protocol (PP) Population

The PP population consists of a subset of the RSV Infected population, and excludes those subjects who have had a major protocol deviation that could potentially impact the primary efficacy endpoint (please refer to 19.3 Appendix C for more details). The subjects will be classified as treated when using this population.

### 5.1.7 Extensive PK Population

The Extensive PK population consists of subjects with consent for extensive PK assessments who have 3 PK assessments done.

## 5.2 Treatment Regimen

For baseline characteristics, efficacy parameters and pharmacodynamics data, the treatment group as assigned by the randomization system will be used in the analysis (i.e., as-randomized analysis).

For prior/concomitant medication, exposure, safety and immunogenicity parameters, the treatment that was actually administered to the subject will be applied in the analysis (i.e., as-treated analysis).

In case a subject in the Placebo group received active study medication, the subject will be assigned to the lowest active treatment group the subject received as actual treatment and analyzed accordingly for the as-treated part of the analysis.

For subjects who received active study medication from more than one active treatment group, the actual treatment group will be set equal to the treatment group assigned by the randomization system, if one of the active doses received is the same as the treatment group the subject has been randomized to; otherwise the actual treatment group will be set to the lowest active treatment group the subject received for the as-treated part of the analysis.

For subjects randomized to active study medication who only received placebo, the actual treatment group will be set to placebo.

Differences between as-treated and as-randomized will be flagged in the listing on subject allocation.

### 5.3 Key Definitions

#### 5.3.1 Definition of baseline

Baseline is defined as the last non-missing assessment before first administration of study drug.

#### 5.3.2 Change from baseline

Absolute change from baseline will be calculated for all post-baseline time-points as:  
[Change from baseline at timepoint t]=[actual value at t] – [Baseline value]

Percent change from baseline will be calculated as:  
[% change from baseline at timepoint t]=[[[actual value at t] – [baseline value]] / [baseline value]]\*100

If baseline value is missing both change from baseline and percent change from baseline will be set to missing.

#### 5.3.3 Imputation of missing data

##### 5.3.3.1 Safety data

Analysis of safety data will be done on observed cases only.

##### 5.3.3.2 Efficacy data: Last observation carried forward (LOCF)

For a large part the efficacy analysis will be done on observed cases, only a limited number of missing data will be imputed (please refer to Section 14.2 for more details). For endpoints with an LOCF imputation, no observed case analysis will be performed.

For LOCF imputation, missing post-baseline values are imputed by the last nonmissing preceding value (including the baseline value). Baseline values are not imputed because per definition, it is the last available pre-dose value. See example below:

	Baseline	...	Day 1	Day 2	Day 3	Day 4
Case 1	Value1	...	Value2	Missing: imputed by Value 2	Missing: imputed by Value 2	Missing: imputed by Value 2
Case 2	Missing: not imputed	...	Value2	Value3	Value4	Missing: imputed by Value 4

### 5.3.4 Time to event

Time to event is defined as the time from the reference point (mostly first dosing) to the first occurrence of the event under consideration.

The censoring mechanism will be described for each time-to-event endpoint separately.

## 5.4 General Methods

### 5.4.1 Summary statistics

For continuous variables, descriptive statistics will be presented. Descriptive statistics will include the number of non-missing data points (n), the arithmetic mean, the standard deviation (SD) (for baseline summaries) and standard error (SE) (for post-baseline or change from baseline summaries), the median, minimum and maximum.

Descriptive statistics of the baseline global severity score (GSS) will additionally include quartiles (Q1 and Q3).

Descriptive statistics of the pharmacodynamic parameter Krebs von den Lungen-6 (KL-6) and of the study drug concentrations by ADA and Nab subject classifications will additionally include 5% and 95% percentiles, geometric mean, geometric SD and coefficient of variation (CV)% of arithmetic mean.

For categorical variables, frequency tabulations will be presented, consisting of frequency counts and percentages. Missing observations (counts) will be tabulated as a separate category but not taken into account for calculating percentages (denominator for percentages is total of non-missing observations within the group). Both zero count categories (rows) within a parameter as well as treatment groups without counts/events (columns) will be shown in the tables .

#### 5.4.2 Graphical representation

For graphs showing mean values, standard error bars will be shown.

#### 5.4.3 Reporting precision

Reporting precision will be driven by the number of significant digits of the original result, unless specifically mentioned.

#### 5.4.4 Statistical significance

For inferential testing, p-values will be referenced against a significance level of 5% ( $\alpha=0.05$ ) unless specified otherwise.

#### 5.4.5 Handling of outliers

No special data handling is foreseen for outlier values.

#### 5.4.6 Totals over groups

Grand total, pooling all subjects, will be displayed only in the tables on subject disposition, demographic and baseline characteristics. A total over all active groups (ALX-0171 Total) will be shown for all safety and efficacy tables unless mentioned otherwise in the description. Outputs will not be presented separately by cohort.

### 5.5 Software and validation model

#### 5.5.1 Software

SAS version 9.2 will be used for programming.

#### 5.5.2 Validation model

Currently valid ████████ STAT SOPs will be followed.

The ADaM datasets and tables related to primary and secondary efficacy endpoints will be validated through independent programming;

Apart from primary and secondary efficacy endpoints all other ADaM datasets, tables, listings and figures will be validated by review of the output, source code and program log by an independent person (i.e., somebody different from the developer).

## 6 GENERAL CHARACTERISTICS

A detailed list of tables and listings can be found in Section 16.1 and Section 18.1, respectively.

## 6.1 Subject Disposition

Subject disposition will be listed and summarized. The summary tables will be presented by treatment group and overall for the all screened population. This includes the number and percentage of subjects in each of the analysis populations defined in Section 5.1. The number and percentage of subjects by country and site will be summarized by treatment group and overall for the ITT population. The number and percentage of subjects who completed the study drug/trial and who prematurely discontinued will also be summarized for ITT population, along with the primary reasons for discontinuation of study drug/trial.

The number and percentage of screen failures will also be summarized along with the primary reason for screen failure.

## 6.2 Protocol Deviations and Eligibility Criteria

A protocol deviation is any change, divergence, or departure from the study design or procedures defined in the protocol. Major protocol deviations concern criteria and disease characteristics that are critical to define the study population and criteria that determine or influence clinical endpoints or criteria that may cause immediate hazard to the subjects (impact on subjects' rights, safety or well-being) or increase the risk to subjects.

The list of (potentially) major protocol deviations will be reviewed by the sponsor and finalized prior to database lock. Detailed information can be found in the trial specific major protocol deviation criteria list.

Major protocol deviations will be tabulated for the mITT population according to their category:

- Selection criteria not met
- Subject not withdrawn as per protocol
- Treatment non-compliance
- Prohibited concomitant medication
- Efficacy assessment deviation
- Safety assessment deviation
- Other

Additionally, major protocol deviations will be listed. Subjects without any major protocol deviation will not be included in the listing.

Subjects with major protocol deviations that could potentially impact the primary efficacy endpoint will be excluded from the PP Population. A detailed list of protocol deviations that will lead to exclusion from the PP population can be found in Appendix C: Major Protocol deviation criteria with potential impact on primary efficacy.

The major protocol deviations that lead to exclusion from the Per Protocol population will be tabulated for the RSV Infected population.

### 6.3 Demographic and Baseline Characteristics

The following demographic and baseline disease characteristics will be summarized descriptively (as defined in Section 5.4) using the following analysis populations:

- Modified intent-to-treat population
- RSV Infected population
- Per Protocol population

Additionally demographic and baseline disease characteristics will be listed

#### Demographic parameters:

- Gender at birth: male / female
- Age at the moment of signing the ICF (months): the age is not recalculated when already available in the database. Following rounding to a fraction of 0.25 will be applied (if calculated):
  - $\leq 1$  month : 1.00 months
  - x months+0-6 days : x.00 months
  - x months+7-13 days : x.25 months
  - x months+14-20 days : x.50 months
  - x months+21-30 days : x.75 months
- Age category: <6 months, 6 - <12 months and  $\geq 12$  months
- Gestational age (weeks)
- Race: not allowed to ask per local regulations / white / black or African American / Asian / American Indian or Alaska native / native Hawaiian or other Pacific islander / other
- Ethnicity: not allowed to ask per local regulations / Hispanic or Latino / non-Hispanic or non-Latino
- History of atopy in 1st grade family
- Exposure to tobacco
- Exposure to pets
- Breastfed
- Height (cm)
- Weight (kg)
- Weight category (3.0 to <4.0, 4.0 to <5.0, 5.0 to <7.0, 7.0 to <10.0, 10.0 to <12.0, 12.0 to <15.0 kg)

#### Baseline disease characteristics:

- RSV diagnosis (test method, test result)
- RSV signs and symptoms
- Number of days between symptom onset and first dose of study drug
- RSV severity criteria :
  - Number of subjects with inadequate oral feeding,
  - Number of subjects with inadequate oxygen saturation,

- Number of subjects with respiratory distress,
  - Number of subjects with inadequate feeding and inadequate oxygen saturation,
  - Number of subjects with inadequate feeding, inadequate oxygen saturation and respiratory distress.
- 
- Global Severity Score (GSS)
  - RDAI score
  - Number of subjects on oxygen supplementation

A listing for above mentioned demographic parameters and another for these baseline characteristics related parameters will be produced for all subjects in the mITT population.

The 19 viral screening tests performed at Baseline (please refer to 19.4 Appendix D for the list of viruses/bacteria tested) and their result (positive or negative) will be tabulated together with general subgroup classification (RSV only or Co-Infected) and will also be listed individually.

#### **6.4 Medical History**

Medical history will be tabulated by (sub)category and additionally listed for the mITT population.

#### **6.5 Prior and Concomitant Medications**

All prior and concomitant therapies will be coded using the latest WHO-DRUG version, and classified using Anatomical therapeutic chemical classification system (ATC level 4 class).

Medications will be classified as prior or concomitant, as reported in the CRF. Prior medications are medications which ended before the signing of informed consent. Concomitant medications are medications which are ongoing at signing of informed consent or which started after the signing of informed consent.

Prior and concomitant therapies will be tabulated by ATC level 4 class and generic term using the safety population. Multiple records of the same generic term for the same subject and ATC level 4 class will be counted only once. The table will therefore present subjects, not occurrences. The tables will be sorted by decreasing frequency (overall). Additionally, all information will be listed.

#### **6.6 Exposure to Study Medication**

The number of subjects in the safety population receiving study medication by day (and nebulization) will be tabulated.

Additionally, exposure and compliance related data including administration information like:

- Administration fully done
- Inhalation period interrupted
- Contact with the face mask
- Resistance to study drug administration
- Crying during nebulization
- Problem occurrence during use of the device

will be tabulated per each nebulization and listed together with any comments on administration events.

The study treatment compliance will also be summarized.

Compliance will be calculated as:

$$\text{Compliance (\%)} = [(\text{number of actual doses})/(\text{number of planned doses})] * 100$$

Any nebulization that was initiated will be considered as actual dose, even if it was not fully administered. Calculation of planned doses will take into account the on-treatment period (up to discontinuation of the subject).

## 7 EFFICACY

A detailed list of tables, listings and figures can be found in Section 16.2, Section 17.2, and Section 18.2 respectively.

### 7.1 Primary Efficacy Endpoint Evaluation

The primary endpoint for this trial is the time needed for the viral load to drop below the plaque assay quantification limit (time-to-BQL) in nasal mid-turbinate swab specimens. Time to BQL is defined as the time from the reference point (first dosing) to the first occurrence of a value below the limit of quantification, provided the next measured value is below the limit as well. The time to event for subjects with missing data and/or who did not reach BQL during the trial will be censored at the last nonmissing viral load assessment .

The time-to-BQL will be compared between each of the ALX-0171 treatment groups and the combined placebo group using a log-rank test. The null hypothesis of this test assumes no difference in time-to-BQL between Placebo and ALX-0171 treated subjects. The tests will be performed in a sequential way to preserve the family-wise error rate at 0.05. Specifically, dose 3 (highest dose) of ALX-0171 will first be tested against the combined placebo group at the 0.05 significance level. Dose 2 of ALX-0171 will only be compared to placebo at the 0.05 significance level if the comparison of dose 3 with placebo is significant. Consequently, dose 1 of ALX-0171 will only be compared to placebo at the 0.05 significance level if the comparison of dose 2 of ALX-0171 with placebo is significant. The primary efficacy endpoint will be evaluated using the mITT population.

The logrank test is based on the assumptions that censoring is unrelated to prognosis and the event probabilities are the same for subjects recruited early and late in the study. Kaplan-Meier (KM) estimates on time-to-BQL will be tabulated (Median, 25th, 75th percentile with confidence interval and general information on censoring) and a graph of the Kaplan-Meier survival curve will be presented.

The data will also be analyzed using a Cox proportional hazards regression model with time to BQL as dependent variable, and treatment group, viral load at baseline and co-infected subject group as independent variables. The hazard ratio (HR) from the Cox model along with the 95% CI will be reported. This analysis will only be performed for the treatment groups where the comparison was significant as analyzed by the log rank test.

For sensitivity analyses, the primary endpoint will also be evaluated using:

- the RSV Infected population
- the Per Protocol population.

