### **3.1.2. STUDY RATIONALE AND DISCUSSION OF STUDY DESIGN**

Safety and tolerability of ALX-0171 have been evaluated in 3 Phase 1 studies in adults, and in a Phase 1/2a study in infants and young children hospitalized for RSV LRTI. Study ALX0171-C201 will include a similar population and aims primarily to evaluate the anti-viral effect of three doses of inhaled ALX-0171, as well as to assess the safety and clinical activity (see section 3.3.2 for dose selection rationale). The outcome of this dose ranging study will support the selection of the optimal dose and the most relevant endpoints for further clinical development.

Study ALX0171-C201 will start with a stepwise assessment of cohorts of 12 subjects, each being randomized in a 3:1 ratio to increasing doses of ALX-0171 or placebo (i.e., 9 subjects receiving ALX-0171 and 3 receiving placebo in each cohort). To guide dose escalation, stopping criteria have been included in the protocol (section 3.1.1). In addition, after each of these 3 sequential cohorts, recruitment will be paused in order to allow the IDMC to evaluate available cumulative safety data and recommend whether the subsequent cohort can be initiated and which planned dose levels can be taken forward into the parallel part. When these initial cohorts have been completed and safety has been confirmed, the study will continue with a parallel allocation to ALX-0171 or placebo. 144 eligible subjects will be randomly assigned in a 1:1:1:1 ratio to 1 of the 4 treatment groups (3 active groups and 1 placebo group).

The design of Study ALX0171-C201 allows an approach with a placebo-controlled group as representative comparison for the three active dose levels. The total volume and corresponding inhalation times of study drug per weight category is similar in all dosing groups, by using a combination of placebo and ALX-0171 (if applicable), administered via

2 serial nebulizations. This ensures blinding across the treatment groups (also see section 3.3.7).

The primary objective of the study is evaluation of the anti-viral effect of ALX-0171 compared to placebo.

As pharmacologically active doses will be used, clinical activity of ALX-0171 will be evaluated in order to assess if the pharmacological effect translates in clinical benefit to the subject. Other objectives include evaluation of pharmacokinetics, pharmacodynamics (biomarker), and immunogenicity.

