#### *Rationale for Sample Size*

The sample size calculation is based on statistical considerations for the analysis of the primary endpoint. With 45 subjects per arm, 85% power is achieved to detect a 50% reduction in median time-to-BQL (0.5 day with ALX-0171 versus 1 day with placebo) for the plaque assay using a two-sided log-rank test at significance level of 0.05. For each comparison of the ALX-0171 dose groups with placebo, a significance level of 0.05 is assumed. For multiple pairwise comparisons, the family-wise error rate is controlled at 5% through the closed testing principle, where the comparison of the lower dose of ALX-0171 to placebo is only performed if the comparison of the higher dose of ALX-0171 to placebo is significant. The sample size calculation also assumes a drop-out rate of 15% to account for subjects dropping out prior to reaching the primary endpoint, or due to a false positive RSV test.

Change from baseline in Global Severity Score is a secondary endpoint of interest in this study. With this sample size, a power of 80% is achieved to detect a difference of 2 points

in the mean change from baseline (to Day 2 post-dose) on the Global Severity Score for each of the ALX-0171 dose groups to placebo. This is based on a two-sided t-test with a significance level of 0.05 and assuming a common standard deviation of 3.2 in each group.

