### **3.3.2. SELECTION OF DOSES IN THE STUDY**

For the first-in-infant pediatric study (Study ALX0171-C104), dose determination was based on a modelling approach, complemented by additional experiments that generated data specifically for administration of ALX-0171 with the FOX-Flamingo inhalation system. Physiologically-based PK modelling was considered the best approach to bridge nonclinical, human adult and human pediatric PK parameters, taking into account growth and developmental processes such as organ maturation, changes in blood flow, body composition, and ontogeny of elimination mechanisms [21, 22]. Based on this approach, a dose of 1.2 mg/kg was chosen for evaluation. The results of study ALX0171-C104 indicated that this dose was well tolerated in all age groups (1 to 24 months). Reductions in nasal viral load (obtained from nasal swabs) were noted, confirming that ALX-0171 can exert antiviral activity when relevant concentrations are achieved. Although the first-in-infant

study was not designed to demonstrate clinical effect, first assessments indicated that the desired level of clinical efficacy was not reached with the administered dose. This was in line with the observation of lower than expected serum concentrations of ALX-0171 which could be indicative of insufficient drug concentrations in the lung, an important site of RSV replication and the driver for clinical effect.

In order to assess a dose response in Study ALX0171-C201, three doses (target dose of 3 mg/kg, 6 mg/kg and 9 mg/kg) will be investigated. At the beginning of the study, 3 sequential safety cohorts of 12 subjects each will be enrolled, with predefined stopping criteria and IDMC assessment before proceeding to the next higher dose.

This dose range will provide information on the PK, PD and clinical outcomes across a relevant range, is expected to provide a potential benefit to the patients, and is intended to determine the optimal dose of ALX-0171 for further clinical development. In view of the favorable safety profile of ALX-0171 in nonclinical and clinical studies and the plasma drug concentrations in the prior study, the doses in Study ALX0171-C201 are considered appropriate to further explore clinical effect. Anticipated systemic concentration to ALX-0171 at the highest dose is estimated to be similar or lower than those obtained in human adult volunteer studies, and maintains at least a 10-fold safety margin compared to nonclinical safety studies.

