### 3.3.7. STUDY DRUG ADMINISTRATION

Three dose levels are planned to be evaluated. The precise dose that will be administered depends on the subject's weight: the drug volume filled into the nebulizer (nominal dose range) is calculated per weight category range (see [Table 1](#)).

- Dose 1: target dose of 3.0 mg/kg (depending on the subject's weight category, the actual nominal dose is between 2.5 and 3.6 mg/kg)
- Dose 2: target dose of 6.0 mg/kg (depending on the subject's weight category, the actual nominal dose is between 5.0 and 7.1 mg/kg)

- Dose 3: target dose of 9.0 mg/kg (depending on the subject's category, the actual nominal dose is between 7.6 and 10.7 mg/kg)

Study drug is administered via inhalation of an aerosol generated by the FOX-Flamingo inhalation system. Detailed instructions for study drug administration are available in the manual concerning study drug.

Study drug administration should start within 3 hours following randomization. Subsequent doses of study drug will be administered at 24-hour intervals ( $\pm$  4 hours) relative to the first dose.

No premedication is required or recommended per protocol, but an inhaled  $\beta$ 2-agonist may be administered at the discretion of the treating Investigator.

Study drug will be administered via inhalation using 2 serial nebulizations. In the placebo group, subjects will receive 2 nebulizations of placebo. In the ALX-0171 dose 1 and 2 groups, subjects will receive 1 nebulization of ALX-0171 and 1 nebulization of placebo. In the ALX-0171 dose 3 group, both nebulizations will contain ALX-0171.

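### The three doses are there to assess a dose response, but no planned efficacy analysis tests or models one, and adjusted hazard ratios are given only for doses that pass their log-rank test

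*SAP*

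**What the plan says.** Protocol 3.3.2 gives the reason for the three active arms: "In order to assess a dose response in Study ALX0171-C201, three doses" will be investigated. Protocol 3.1.2 adds: "The outcome of this dose ranging study will support the selection of the optimal dose and the most relevant endpoints for further clinical development".

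For time-to-BQL, SAP 7.1 plans this: "The time-to-BQL will be compared between each of the ALX-0171 treatment groups and the combined placebo group using a log-rank test". Testing runs from the top dose down: "Dose 2 of ALX-0171 will only be compared to placebo at the 0.05 significance level if the comparison of dose 3 with placebo is significant", and dose 1 follows dose 2 under the same rule. SAP 7.1 then adds a Cox model with treatment group, baseline viral load and co-infection as independent variables, but with a restriction: "This analysis will only be performed for the treatment groups where the comparison was significant as analyzed by the log rank test".

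SAP 7.1 to 7.4 and the index of tables contain no trend test, dose-response model or named contrast between active doses for any efficacy endpoint. SAP section 13, which lists additions to the protocol analysis, does not add one. Neither document states a rule for selecting the dose.

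**The concern.** Three dose-versus-placebo tests answer whether each dose beats placebo. They do not say whether 9 mg/kg does more than 6 or 3 mg/kg, which is what a dose-response aim needs. The Cox restriction adds to the gap. If dose 3 misses, the text of SAP 7.1 yields no adjusted hazard ratio for any dose, so the covariate-adjusted effect estimates are missing just when a reader would most want to compare the arms. At stake is how well the trial can inform its own stated question: whether a lower dose does as much as a higher one, or whether the effect is still rising at the top of the range.

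**Working it through.** **Reproducing the plan's sample size.** Protocol 3.1.2 states: "With 45 subjects per arm, 85% power is achieved to detect a 50% reduction in median time-to-BQL", from 1 day to 0.5 day, two-sided 0.05, with 15% drop-out. Under exponential times the hazard ratio for reaching BQL is 1/0.5 = 2.

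- Events per pair (Schoenfeld) = 4(1.960 + 1.036)² / (ln 2)² = 74.7, so 75, or 38 per arm.
- 38 / 0.85 = 44.7, so 45 per arm. This matches.
- Back-check: 2 × 45 × 0.85 = 76.5 events give 85.8% power.

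**Power for one dose against another at this size.** Power = Φ(√(76.5/4) × ln HR − 1.96):

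| Hazard ratio between two doses | Power |
|---|---|
| 2.0 | 86% |
| 1.59 | 53% |
| 1.41 | 32% |
| 1.26 | 17% |

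Direct comparisons of doses are therefore weak unless medians differ about two-fold.

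**What the planned sequence shows about shape.** The documents give no curve, so three were assumed.

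- 38 evaluable children per arm, exponential times, placebo median 1 day.
- Each time is rounded up to the next swab at 5, 22, 29, 46 or 50 hours or Day 14.
- Tests are two-sided at 0.05.
- The linear curve has log-hazard proportional to dose: 2^(1/3) = 1.26 and 2^(2/3) = 1.59.
- Slopes are score tests on target dose (0, 3, 6, 9).

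| Assumed HR v placebo at 3 / 6 / 9 mg/kg | Dose 3 misses, testing ends | Some but not all doses pass | All three pass | Four-arm slope rejects | Active-arm slope rejects |
|---|---|---|---|---|---|
| Plateau 2 / 2 / 2 | 22% | 78 − 59 = 19% | 59% | 77% | 5% |
| Linear 1.26 / 1.59 / 2 | 22% | 78 − 11 = 67% | 11% | 83% | 45% |
| Steep 2 / 2.86 / 4 | about 0% | 100 − 79 = 21% | 79% | about 100% | 76% |

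Under no effect, the four-arm slope rejects in 5%. Independent repeats agreed to within a few points. Without the swab grid, all three doses pass in about 68% (plateau) and 83% (steep).

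**Reading the table.**

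- The most likely result, all three passing, is the same for a flat curve and for one where the top dose clears virus twice as fast as the lowest. About one plateau trial in five gives a partial pass that looks like a rise.
- The pattern is not empty of information: all three pass far less often under the linear curve (11%) than under the plateau (59%).
- The active-arm slope is the quantity that separates flat from rising (5% against 45% and 76%). The four-arm slope does not separate plateau from linear (77% against 83%).

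**If the top dose is weaker.** With medians of 0.55, 0.5 and 0.7 day at doses 1, 2 and 3 (no swab grid), testing stops at dose 3 in 66% of trials, although dose 2 alone has 84% power and dose 1 has 72%. Under the SAP text no adjusted hazard ratio would then be reported.

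**The case against.** The strongest reply is that the primary analysis fits the primary objective, which is anti-viral effect compared with placebo. Fixed-sequence testing from the top dose is a recognised way to hold the family-wise error rate, and losing the lower doses after a miss is its accepted cost. The dose-response wording sits in the rationale, not in the list of objectives. All of this stands, and it is why the confirmatory sequence should stay as it is. It does not explain why a stated reason for having three doses has no matching efficacy analysis.

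A reader might infer that nothing in the plan compares or models the doses. The documents do not support that:

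- SAP Appendix B regresses serum concentration on dose group, using sequential-part data.
- Protocol 3.6.6 plans a population PK model.
- SAP 7.2.1 reports pair-wise GSS comparisons outside the testing sequence.

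The first two do not link dose to efficacy in the documents supplied, and the separate Data Analysis Plan is not among them. The GSS pairs are unnamed, while Protocol 3.6.5.2 mentions only active dose against placebo.

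A reader might also infer that the dose would be chosen by counting significant arms. Neither document says so. Kaplan-Meier quartiles with confidence intervals, viral load profiles, GSS, clinical response, safety and PK results will be available by dose whatever the tests show. For time-to-BQL, however, those results are descriptive and give no slope or contrast between doses.

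Two limits on any remedy also stand. A non-significant active-arm slope is not evidence of a plateau: at 45% power, 55% of truly linear curves would fail to reject. And mg/kg within an arm is fixed by body weight and the fill volumes in Protocol Table 1, so that variation is not randomised and is confounded with weight and age.

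**Conclusion.** The point holds as a gap between stated purpose and planned efficacy analysis. No planned efficacy analysis tests or models the dose-response relationship, and adjusted hazard ratios for the primary endpoint depend on passing the log-rank sequence. That sequence is valid for its own claims but does not show the shape of the curve: all three doses pass in about 59% of plateau trials and 79% of steep-rise trials, and testing stops at dose 3 in about 22% of plateau trials.

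These percentages rest on assumed curves, exponential times, 38 evaluable children per arm and an assumed swab grid. They do not model the requirement that the next value also be below the limit. The absence of the analysis rests on the text alone. The confirmatory result is not at risk. This is a worthwhile, low-cost improvement.

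**What to change.** In SAP 7.1, add a supportive analysis outside the confirmatory sequence, reported whatever the log-rank results:

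1. Fit one Cox model with all four arms and the SAP's own covariates (baseline viral load, co-infection). Report the hazard ratio against placebo with 95% CI for every dose, and remove the restriction to significant groups.
2. Report the slope per randomised target dose (0, 3, 6, 9 mg/kg) over all four arms, and the slope within the three active arms, each with a 95% CI.
3. State that the active-arm slope is an estimate with limited precision (about 45% power under a linear log-hazard with hazard ratio 2 at 9 mg/kg), and that a non-significant slope is not to be read as a plateau.
4. Use individual nominal mg/kg, if at all, only as a sensitivity analysis adjusted for weight and age.

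In SAP 7.2.1, name the GSS pairs. No rule tying dose selection to the slope is proposed.

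The cost is SAP wording and a few model runs on data already collected. The confirmatory alpha is unchanged. The downside is a wide interval for the active-arm slope, which has to be reported as such.
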